6.4.6 Appropriate Specific Medical Care Address after the Clinical Investigation

[figure not shown]
NA

6.4.7 Recommended Follow-Up Address after the Clinical Investigation

NA

6.4.8 Final Disposition or Potential Future Use of Samples obtained from Patients Address

All biological samples (tear samplings) that have already been collected may be retained and analysed at a later date, per local regulations (e.g. for potential post study genomic analysis).

6.5.1 Source Documents

Each participating investigational site will maintain appropriate medical and research records in compliance with GCP (ISO 14155 current version) and any other regulatory and institutional requirements for the protection of patient's confidentiality.

Source data are all information in original records and certified copies of original records of clinical findings, observations, or other activities in a clinical investigation necessary for the reconstruction and evaluation of the clinical investigation. Source data are contained in source documents.

Source documents are any original documents, data and records. These may include, but are not limited to, patient medical records, hospital charts if any, clinic charts, laboratory notes, patient's questionnaires, patient's diaries if any, the investigator's files, pharmacy dispensing records and recorded data from automated instruments.

Some specific medical data gathered during routine medical practice visits prior to the participation can be used in screening visit and before informed consent form on the patient best care interest.

All following patient's assessments will be collected via a paper diary and paper questionnaire and will be considered as source data:

- Run-in treatment compliance: number of instillations/day
- IMD compliance: number of instillations/day
- OSDI questionnaire
- DEAL questionnaire
- VAS

The following information should be entered into the patient's medical record:

- Patient's name, date of birth, gender
- Patient's contact information
- The date the patient entered the clinical investigation and patient's number
- The study title and/or the clinical investigation number
- A statement that informed consent was obtained (including the date) and patient's card was provided to the patient; data protection consent or other country and local patient privacy required documentation for this investigation have been obtained (including the date)
- Date of all patient's visits
- Investigated disease history:
 - o Diagnosis of DES for each eye
 - o Date of onset of the diagnosis in each eye (months/year)
 - o Previous use of artificial tears
- Ocular and systemic medical and surgery history (other than dry eye)

For systemic medical history, the information could be collected via patient interview. For ophthalmic medical history of referred patient's, a letter from the referring ophthalmologist is strongly recommended.

- Prior and concomitant medications (list all prescription and non-prescription medications being taken at the time of enrolment and within 3 months before screening visit). At each subsequent visit, changes to the list of medications should be recorded.
- Name/initials and signature of the persons who perform assessments
- Visual acuity values (standard BCVA value with used chart name)
- Slit-lamp examination results with score of ocular signs, conjunctival hyperaemia, corneal staining by fluorescein and conjunctival staining by fluorescein with a yellow filter and TBUT
- Shirmer test results for both eyes
- Occurrence and status of any AEs
- Occurrence and status of any incident
- Review of inclusion/exclusion criteria and patient's status (confirmation of patient eligibility or not, reason for screen failure if applicable)
- Ocular tolerance and performance assessment by Investigator
- Tolerance and performance assessment by the patient
- Information on diary dispensation to the patient and instructions correctly provided
- Information on Run-in treatment dispensation, instruction for use and kit number provided to patient
- Information on IMD dispensation, including kit number assignment with IRT notification
- Run-in treatment compliance collected by reviewing patient's diary and interview and checked against returned kit
- IMD compliance collected by reviewing patient's diary and interview and checked against returned IMD
- Information on used/unused IMD by patient, assessed by unmasked collaborator
- The date of the patient exited the clinical investigation and a notation as to whether the patient completed the clinical investigation or reason for discontinuation.

6.5.2 Source Data Verification

One of the primary responsibilities of monitoring is the Source Data Review (SDR) to check quality of source, review CIP compliance, ensure the critical processes and source documentation are adequate, to ascertain Investigator involvement and appropriate delegation and assess compliance to other areas (e.g; SOPs, GCP, ISO 14155 current version). This will require direct access to all source documents, any original documents, data and records of each patient.

It will be verified that informed consent documentation is filed for all screened patients whether or not they were randomised into the clinical investigation and that the information is listed in the source documents.

Source Data Verification (SDV) will be recorded in e-CRF and SAE/pregnancy related documents, consisting in a comparison of the source documentation and other records relevant to the clinical investigation/ with the e-CRF. This will require direct access to all source documents, any original documents, data, and records of each patient.

The SDV will ensure the data are Attributable, Legible, Contemporaneous, Original, Accurate, Complete, Consistent, Enduring and Available (ALCOACCEA guiding principles).

Source Data Monitoring combines:

- ✓ Site Monitor review of the source data for a patient in order to confirm that the site is compliant with ICH GCP, ISO 14155 current version and the CIP.
- ✓ Evaluation of the conformity of the data presented in e-CRF, or other Sponsor-provided documents, with the available Source Data.

SDR can be done alone, but SDV cannot be done without prior SDR, since validating data transcription is not useful if CIP and GCP, ISO 14155 current version compliance have not been confirmed first.

6.5.3 Case Report Forms

The patients will be monitored throughout the clinical investigation and all results of evaluations will be recorded in an e-CRF.

The e-CRF completion guidelines will be provided and introduced to the investigation staff before the start of the clinical investigation.

The investigator and authorised delegate(s) will have secured access to enter the data in the appropriate sections of the e-CRF and to IRT.

The e-CRF must be completed for each patient screened in the clinical investigation, including screening failure patients. It should be completed as soon as possible after the patient visit.

The investigator is required to prepare and maintain adequate and accurate ocular and systemic history designed to record all observations and other data pertinent to the investigation for each patient.

The investigator is responsible for ensuring that data are properly recorded on each patient's e-CRF and related documents.

The investigator will be responsible for the punctuality, completeness, consistency and accuracy of e-CRF. E-CRF and source data will be retained by the investigator for data verification at each scheduled monitoring visit.

The principal investigator or delegate(s) should personally electronically validate and sign e-CRFs to ensure that the observations and findings are correctly and completely recorded on the e-CRFs.

All information recorded on the e-CRFs for this clinical investigation must be consistent with the patients' source documentation (i.e., medical records).

A copy of completed e-CRFs pages and incident forms will be stored in the investigator's archives for at least 10 years after the last T2769 device has been placed on the market.

7 STATISTICAL DESIGN AND ANALYSIS

The Statistical Analysis Plan (SAP) will provide, before locking the database and breaking the blind, detailed methods for the analyses outlined below.

Any changes from the planned analyses will be described and justified in the final CIR.

7.1 ANALYSIS POPULATION AND PROCEDURES

The following analysis sets will be considered:

- **Safety set:**

All enrolled patients, having received at least one dose of IMD. Patients will be analysed according to the treatment received.

Safety set will be the primary population for safety analysis.

- **Intent-to-Treat (ITT) set:**

All randomised patients. Patients will be analysed according to the treatment they were assigned to at randomisation.

- **Full Analysis Set (FAS):**

All randomised patients having received at least one dose of IMD, with at least one baseline and one post-randomisation performance assessment. Patients will be analysed according to the treatment they were assigned to at randomisation.

- **Per protocol (PP) set:**

Subset of the FAS including patients without any major CIP violations likely to seriously affect the primary outcome of the study. Patients will be analysed according to the treatment received.

The FAS will be the primary population for performance analysis. The PP set will be considered as the secondary population and will be used for sensitivity analyses of the primary  performance endpoint.

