6.3.8 Number of Patients Required to be Randomised in the Clinical Investigation

It is planned to randomise 74 patients in order to have 68 evaluable patients (34 per group) for the FAS analysis.

Evaluable patients will be defined as randomised patients having received at least one dose of IMD and with at least one performance endpoint post-randomisation visit.

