7.2.1 Performance Analyses

Primary [REDACTED] performance endpoint will be primarily analysed on the FAS. Sensitivity analysis of the primary [REDACTED] performance endpoint will be performed on the PP.

The detailed analysis methods for primary and each secondary performance variables will be discussed further in the SAP.

[figure not shown]
Primary performance endpoint

[figure not shown]
The primary performance endpoint is the change from baseline (D1) in total ocular surface staining grade according to Oxford 0-15 grading scheme at D36 in the study eye. The analysis will be performed following original Oxford scale [REDACTED]

The inferential analyses of the primary performance endpoint will aim to assess the non-inferiority of T2769 to Hylo-Forte®. The hypothesis of non-inferiority will be tested by calculating the bilateral 95% CI around the difference between groups (T2769 – Hylo-Forte®) in mean change from baseline in the total ocular surface staining (Oxford score) to D36 in the study eye. If the upper bound is no higher than +2 points, it will be concluded that the null hypothesis can be rejected and that the performance of T2769 is non-inferior to that of Hylo-Forte®.

The non-inferiority will be primarily tested using a Mixed Model for Repeated Measures (MMRM) approach. The model will include treatment and scheduled visit time points (D15 and D36) as fixed factors, patient as random factor, and baseline total ocular surface staining (Oxford score) as continuous covariate Treatment by scheduled visit time point and baseline total ocular surface staining (Oxford score) by scheduled visit time point will be included as an interaction term in the model.

Descriptive tables will also be produced presenting data for total ocular surface staining values and change from baseline at each visit.

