6.3 Statistical Analysis

6.3.1 Primary Performance Analysis

The primary performance endpoint is the change from baseline (D1) in total ocular surface staining grade according to Oxford 0-15 grading scheme at D36 in the study eye.

will be performed following original Oxford scale

he primary analysis

The inferential analyses of the primary performance endpoint will aim to assess the non-inferiority of T2769 to Hylo-Forte®. The non-inferiority will be primarily tested using a MMRM approach.

The model will include treatment and scheduled visit time points (D15 and D36) as fixed factors, patient as random factor, and baseline total ocular surface staining (Oxford score) as continuous covariate. Treatment by scheduled visit time point and baseline total ocular surface staining (Oxford score) by scheduled visit time point will be included as an interaction term in the model.

Descriptive tables will also be produced presenting data for total ocular surface staining values and change from baseline at each visit to support the MMRM analysis tables.

The mean and associated SD of the Oxford score on the study eye for each treatment will be graphically displayed by analysis visit for the FAS.

[figure not shown]
This document is confidential.

Statistical Analysis Plan

Sponsor: Laboratoires Théa; Clinical Investigational Plan No.: LT2769-004

Primary performance endpoint will be primarily analysed on the FAS. [REDACTED]

[figure not shown]
[REDACTED]

This document is confidential.

Statistical Analysis Plan

[figure not shown]
Sponsor: Laboratoires Théa; Clinical Investigational Plan No.: LT2769-004

This document is confidential.

Statistical Analysis Plan

[figure not shown]
Sponsor: Laboratoires Théa; Clinical Investigational Plan No.: LT2769-004

This document is confidential.

Statistical Analysis Plan

[figure not shown]
Sponsor: Laboratoires Théa; Clinical Investigational Plan No.: LT2769-004

This document is confidential.

Statistical Analysis Plan

Sponsor: Laboratoires Théa; Clinical Investigational Plan No.: LT2769-004

This document is confidential.

[figure not shown]
Statistical Analysis Plan

Sponsor: Laboratoires Théa; Clinical Investigational Plan No.: LT2769-004

This document is confidential.

Statistical Analysis Plan

[figure not shown]
Sponsor: Laboratoires Théa; Clinical Investigational Plan No.: LT2769-004

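### Does resting the non-inferiority conclusion on the FAS, with the PP set only as a sensitivity analysis, leave the primary claim unsound?

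*Protocol*

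**What the plan says.** - **Decision rule.** Protocol 7.2.1 tests by "calculating the bilateral 95% CI around the difference between groups" (T2769 minus Hylo-Forte) in mean change of the Oxford total at D36. "If the upper bound is no higher than +2 points, it will be concluded that the null hypothesis can be rejected". The rule attaches no condition from a second set.
- **Which set decides.** Protocol 7.1: "The FAS will be the primary population for performance analysis". SAP 6.3.1 agrees: "Primary performance endpoint will be primarily analysed on the FAS". The FAS is analysed by assigned treatment.
- **Role of the PP set.** "The PP set will be considered as the secondary population and will be used for sensitivity analyses of the primary" performance endpoint (Protocol 7.1; SAP 5 gives it the same role). It is defined as "Subset of the FAS including patients without any major CIP violations likely to seriously affect the primary outcome of the study" and is analysed by treatment received.
- **Sizing.** "It is planned to randomise 74 patients in order to have 68 evaluable patients (34 per group) for the FAS analysis" (Protocol 6.3.8).
- **Timing.** "The Statistical Analysis Plan (SAP) will provide, before locking the database and breaking the blind, detailed methods for the analyses outlined below" (Protocol 7). SAP 2 places its finalisation before database lock. Protocol 10 has exclusions from the analysis sets discussed at a blind review before lock. Protocol 6.1.2.3 opens the randomisation list only after lock.

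**The concern.** In a superiority trial, deviations usually work against the sponsor. In a non-inferiority trial they can help, because patients who did not follow the plan may show little difference between arms and so move the FAS estimate towards zero. By the PP definition, the FAS patients left out of the PP set are those whose violations are expected to affect the primary outcome seriously. Protocol 6.3.3 shows that such patients can stay in the trial: one who took a prohibited medication may continue, with a deviation recorded.

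Read literally, a FAS limit below +2 yields non-inferiority even if the PP limit lies above +2, and no visible sentence says how to word that result. At stake would be a confirmatory claim that hides a worse effect in compliant patients, with the explanation chosen after unblinding.

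**Working it through.** **Inputs from the documents.** Margin +2, two-sided 95% interval (one-sided 0.025), 34 per group in the FAS, 74 randomised.

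**Assumptions.** SD, power and the expected number of deviations are not visible. I take a true difference of 0 and power of 80% to 90%, and back-solve the SD. A normal approximation stands in for the mixed model.

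**1. The plan's own figure.** 1 − 68/74 = 8.1% loss, and 68/(1 − 0.08) = 73.9, so 74. From n = 2·SD²·(1.96 + z)²/2², 34 per group corresponds to SD 2.54 at 90% power (z = 1.28) or SD 2.94 at 80% (z = 0.84). The visible figures are coherent.

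**2. Error of the rule for the effect it tests.** If the true FAS difference is +2, P(FAS passes) = Φ(−1.96) = 0.025. No inflation.

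**3. Error if the target is instead the effect in compliant patients.** Let that effect be +2 and let a share q of the FAS be deviators with no difference between arms. Then P(FAS passes) = Φ(2q/SE − 1.96), with SE = SD·√(2/34).

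| q | SD 2.54 (SE 0.617) | SD 2.94 (SE 0.714) |
|---|---|---|
| 10% | 5.1% | 4.7% |
| 15% | 7.0% | 6.2% |
| 20% | 9.5% | 8.1% |

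This is the concern at full strength. It needs deviators with exactly zero difference. If they keep half of it, simulation with 3 to 7 deviators per arm gives 3.4% to 5.0% (SD 2.5).

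**4. Discordance with no dilution at all.** The PP set is nested in the FAS, with correlation √(n_PP/34) between the two estimates. At a true difference of 0:

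| PP per arm | FAS pass and PP fail, SD 2.54 | SD 2.94 |
|---|---|---|
| 31 | 4.0% | 5.7% |
| 29 | 6.3% | 8.7% |
| 27 | 9.0% | 11.9% |

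Part of this is width alone. At SD 2.54 the FAS passes with an estimate up to 2 − 1.96 × 0.617 = 0.79. A PP set of 27 per arm needs 2 − 1.96 × 2.54 × √(2/27) = 0.64. The same estimate of 0.75 passes one and fails the other.

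**5. Does a PP fail identify dilution?** At a true +2 with no dilution, FAS pass with PP fail has probability 0.0069, 0.0090 and 0.0106 for 31, 29 and 27 per arm. Divided by 0.025, this is 28%, 36% and 42% of FAS passes. With full dilution the simulated shares are 49%, 64% and 74% (3, 5 and 7 deviators per arm, SD 2.5). Much of the apparent exposure is therefore present without any dilution.

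**6. What the plan already reports.** The PP analysis of the primary endpoint is planned (Protocol 7.2.1, SAP 5). SAP 6.2.1 tabulates patients per analysis set by treatment group, so exclusions per arm follow by subtraction. SAP 6.2.7 summarises exposure and compliance for both FAS and PP.

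**The case for a change.** The strongest opposing case is that reporting a PP result is not the same as saying how it qualifies the conclusion. The trial is confirmatory (Protocol 3.4), a few sentences before lock would cost no power, and discordance cannot be explained reliably after the event. Even without dilution, the PP estimate lies above the FAS estimate in about 92% to 97% of discordant trials, so its direction settles nothing.

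Part of this stands. No discordance wording is visible, and a PP fail does carry information. Among FAS passes with 7 excluded per arm at SD 2.5, it occurs in 74% of fully diluted trials at +2, against 0.091/0.902 = 10% when the products are equal.

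It does not show a fault, for three reasons.

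- The formal conclusion is already fixed by Protocol 7.2.1 and cannot be chosen after unblinding. Only the discussion of a sensitivity result is open. That the report would state non-inferiority without mentioning the PP result is inferred from silence.
- The absence cannot be established. Text is blacked out within the PP definition in SAP 5 and after the FAS sentence in SAP 6.3.1. SAP 6.1.2, on bias and confounding, is in the contents but shows no text. Redacted text does not count as missing.
- A compulsory statement that the PP set did not confirm the result would give that set more weight than a sensitivity analysis. It excludes on events after randomisation and analyses by treatment received, so it is not a clean benchmark. Requiring both sets to pass would lower power from 90% to 86%, 84% or 81%, or from 80% to 74%, 71% or 68%, with 31, 29 or 27 per arm in the PP set.

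**Conclusion.** The concern does not hold. Followed as written, the plan gives a sound conclusion about the as-randomised FAS comparison at one-sided 2.5%, with a planned PP result beside it and PP membership discussed under the blind. The 5% to 9% figures in step 3 answer a different question, the effect in compliant patients, and require deviators with no difference at all. A fixed label for discordant results is a reporting preference on which statisticians differ. With 7 of 34 excluded per arm it would attach to about 9% (SD 2.54) or 12% (SD 2.94) of trials of an equal product.

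The error statement for the FAS does not depend on the unseen SD. All discordance and dilution figures do, and they also rest on the assumed number and behaviour of deviators, so they show scale only.

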7.2 STATISTICAL ANALYSIS

[figure not shown]
Statistical descriptions will be performed by treatment groups. For disposition and demography description will also be presented overall.

Variables recorded for each eye will be described separately for the study eye and for the contralateral eye (if applicable).

Baseline is defined as the assessment at D1 visit before the first IMD instillation. Missing values at randomisation visit will not be replaced.

For endpoints defined as change from baseline, the descriptive statistics by visit (Screening, D1, D15 and D36) and the change from baseline at D15 and D36 will be presented.

Disposition, demographics, exposure, history of dry eye, medical/surgical history (by System Organ Class [SOC] and PT separately for ocular and systemic history), will be summarised by treatment group and overall, for the FAS, PP set and Safety set [REDACTED]. [REDACTED] Disposition and demographics will also be presented for the ITT. Previous and concomitant ocular/non-ocular treatments will be listed.

7.2.1 Performance Analyses

Primary [REDACTED] performance endpoint will be primarily analysed on the FAS. Sensitivity analysis of the primary [REDACTED] performance endpoint will be performed on the PP.

The detailed analysis methods for primary and each secondary performance variables will be discussed further in the SAP.

[figure not shown]
Primary performance endpoint

[figure not shown]
The primary performance endpoint is the change from baseline (D1) in total ocular surface staining grade according to Oxford 0-15 grading scheme at D36 in the study eye. The analysis will be performed following original Oxford scale [REDACTED]

The inferential analyses of the primary performance endpoint will aim to assess the non-inferiority of T2769 to Hylo-Forte®. The hypothesis of non-inferiority will be tested by calculating the bilateral 95% CI around the difference between groups (T2769 – Hylo-Forte®) in mean change from baseline in the total ocular surface staining (Oxford score) to D36 in the study eye. If the upper bound is no higher than +2 points, it will be concluded that the null hypothesis can be rejected and that the performance of T2769 is non-inferior to that of Hylo-Forte®.

The non-inferiority will be primarily tested using a Mixed Model for Repeated Measures (MMRM) approach. The model will include treatment and scheduled visit time points (D15 and D36) as fixed factors, patient as random factor, and baseline total ocular surface staining (Oxford score) as continuous covariate Treatment by scheduled visit time point and baseline total ocular surface staining (Oxford score) by scheduled visit time point will be included as an interaction term in the model.

Descriptive tables will also be produced presenting data for total ocular surface staining values and change from baseline at each visit.

